### ***3.2.3 Vital Signs***

Measurement of vital signs will include an assessment of pulse rate, blood pressure, respiration rate, and temperature. Vital signs will be measured at all study visits, excluding the Follow-up Visit.

Height will be measured at the Screening Visit and weight will be measured at all study visits, excluding the Follow-up Visit.

### ***3.2.4 Electrocardiograms***

ECGs will be performed in triplicate and sent to a central reviewer. A 12-lead ECG will be performed at the Screening Visit and pre-dose on Day 1, Day 14, Day 42, Day 70, and the ET Visit, if applicable. Electrocardiograms will be performed pre-dose and 2 hours post-dose on Day 28, Day 56, and Day 84.

### ***3.2.5 Physical Examinations***

A full PE will be performed at the Screening Visit, Day 84, and the ET Visit, if applicable, and includes genitourinary examination per the Investigator's discretion and does not include a rectal examination. Assessment for xanthoma or arcus should also be part of the full PE.

A symptom-directed PE will be conducted at all other study visits and the Follow-up Visit (only for patients who had an abnormal result at Day 84 [or the ET Visit, if applicable] or an ongoing treatment-related adverse event).

### 3.3 Pharmacokinetic Variables

#### 3.3.1 Concentration Data

Pharmacokinetic samples will be collected pre-dose (must be  $24 \pm 2$  hours from the previous day's dose) and 0.5, 1, 2, 3, 5, and 12 hours post-dose on Day 28, Day 56, and Day 84 in collection tubes containing K2EDTA as the anticoagulant. For all other study visits where routine plasma drug monitoring will be performed (Day 1, Day 14, Day 42, Day 70, and the ET Visit, if applicable), samples will be collected pre-dose (must be  $24 \pm 2$  hours from the previous day's dose if a previous day's dose occurred).

#### 3.3.2 Pharmacokinetic Parameters

The following PK parameters will be calculated, as appropriate, from the individual plasma concentrations of gemcabene on Day 28, Day 56, and Day 84:

- $C_{\max}$ : maximum plasma concentration,
- $t_{\max}$  (h): time to maximum plasma concentration in hours,
- $AUC_{0-t}$  (ng·h/mL): area under the concentration-time curve to the last quantifiable time, and
- $AUC_{0-24}$  (ng·h/mL): area under the concentration-time curve to the 24-hour time point.

## 4 ANALYSIS POPULATIONS

Two analysis populations are designed for the study: the Full Analysis Set (FAS) Population and the Safety Population (SP).

#### 4.1.1 Safety Population

The SP will include all patients who are enrolled into the study and have at least 1 dose of study drug. This population will be used to summarize all safety data.

#### 4.1.2 Full Analysis Set Population

The FAS will include patients from the Safety Population who also have a valid post-baseline efficacy assessment, for a given dose level.

## 5 GENERAL CONSIDERATIONS FOR DATA ANALYSIS

PI [REDACTED] is responsible for the statistical analyses for this trial. The statistical planning and conduct of analyses of the data from this trial will follow the principles defined in relevant International Conference of Harmonisation (ICH)-E9 guidelines and PI [REDACTED] biostatistical standard operating procedures (SOPs). All tables, figures, and listings will be generated with SAS® (SAS Institute Inc., Cary, North Carolina, USA) Version 9.3 or higher and printed using a Rich Text Format (RTF) file format.

### **5.1 Evaluation of Center Effect**

Due to the design, objectives, and sample size of the trial, center effects will not be evaluated.

### **5.2 Assessment Windows**

To summarize laboratory variables, consecutive time windows will be created around each planned visit. In the descriptive statistics of laboratory variables, only measurements from scheduled visits will be used if values are available. If no values from a scheduled visit are available but values from unscheduled visits are available, the values from the last unscheduled visit from that window will be used for the summary statistics. The results of all laboratory values from unscheduled and repeat measurements will be recorded in the clinical database. In listings and narratives, all laboratory values including unscheduled and repeat values will be included.

For analysis purposes, if the event date is on or after the first treatment date, the study day is defined as follows:

$$\text{Study Day} = \text{Event date} - \text{First treatment date} + 1$$

Therefore, the day of first treatment will be Day 1. If the event date is prior to the first treatment date, the addition of 1 will not be included in the calculation; thus, there will be no Day 0.

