10.2.2 Missing Data

The primary analyses of the primary and secondary outcome variables will use linear mixed effects models. This analysis method will allow for inclusion of patients with missing values thus using the maximum amount of data for the analysis and making fewer assumptions about the missing data compared to a more traditional per protocol analysis.

To summarize laboratory variables, consecutive time windows will be created around each planned visit. In the descriptive statistics of laboratory variables, only measurements from scheduled visits will be used if values are available. If no values from a scheduled visit are available but values from unscheduled visits are available, the values from the last unscheduled visit from that window will be used for the summary statistics. The results of all laboratory values from unscheduled and

repeat measurements will be recorded in the clinical database. In listings and narratives, all laboratory values including unscheduled and repeat values will be included.

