APPENDIX E: MUSCLE INJURY AND HEPATIC MONITORING

Muscle Injury

Muscle injury will be assessed using a combination of clinical signs and symptoms and laboratory data (creatinine kinase [CK], hepatic, and renal function).

All patients with suspected or confirmed muscle injury should be managed according to the standard of care at the discretion of the Investigator.

- Patients with new or unexplained muscle symptoms should have an unscheduled visit scheduled within 7 days of site notification. At this visit, samples should be sent for a full chemistry panel, including CK, liver, and renal function.
- Patients with CK elevations of $>3 \times$ upper limit of normal (ULN) who are asymptomatic should be considered for an unscheduled visit (+ isozymes), based upon medical judgment.
- All patients with CK elevations $>10 \times$ ULN should have an unscheduled visit (+ isozymes). Study drug should be temporarily discontinued, pending the results of an investigation into the cause of muscle injury and/or CK elevation is complete.

It is important that patients are instructed to not undertake any form of strenuous physical activity for at least 24 hours prior to repeat blood testing.

Hepatic Monitoring

Patients with hepatic enzyme elevations should be managed according to the standard of care, at the discretion of the Investigator. For patients with signs or symptoms suggestive of hepatitis, an unscheduled visit and a chemistry panel should be performed. Patients with an alanine aminotransferase (ALT) $>2 \times$ ULN with symptoms suggestive of hepatitis should have an unscheduled visit. Patients with ALT $>3 \times$ ULN with or without symptoms should also have an unscheduled visit. A repeat assessment should be performed as soon as possible to confirm the finding. A clinical evaluation should be performed, including assessment of past medical history (including non-alcoholic fatty liver disease/steatohepatitis and alcohol use) and concomitant medications (including over the counter drugs and herbal supplements). Risk factors for hepatitis infection should be reviewed and hepatitis studies should be performed.

Study drug should be temporarily discontinued during this evaluation if the patient has signs or symptoms of hepatitis or an ALT $>5 \times$ ULN. The possible dosing re-initiation (re-challenge) or follow-up schedule for any events meeting these criteria will be determined by the Investigator in consultation with the Medical Monitor.

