## 8 ANALYSIS OF SAFETY

Safety will be assessed using the SP. The assessment of safety will include adverse events, clinical laboratory assessments, ECGs, physical examinations, and vital signs. The safety analysis will be based primarily on the frequency of new or worsening adverse events, laboratory abnormalities, and SAEs. Other safety data will be summarized as appropriate.

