## **8.3 Safety Laboratory Parameters**

Clinical chemistry, coagulation, hematology, and urinalysis results will be summarized with descriptive statistics at all visits with the focus on Day 28, Day 56, and Day 84. Change from baseline will also be summarized. Frequency counts of new or worsening abnormalities will also be provided. Laboratory values will also be listed by visit, within patient.

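### The only stated rule for selecting laboratory values takes scheduled values, or else the last unscheduled one, and the abnormality counts are not exempted, so peaks at unscheduled visits can be missing from those tables

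*SAP*

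**What the plan says.** SAP 5.2 places a window around each planned visit, without giving its limits, and then selects values: "In the descriptive statistics of laboratory variables, only measurements from scheduled visits will be used if values are available". Where the scheduled value is absent, "the values from the last unscheduled visit from that window will be used for the summary statistics". Protocol 10.2.2 has the same rule ("only measurements from scheduled visits will be used if values are available"), so the SAP does not depart from the protocol here.

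The full set of values is assigned to two kinds of output only: "In listings and narratives, all laboratory values including unscheduled and repeat values will be included".

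SAP 8.3 says that the laboratory "results will be summarized with descriptive statistics at all visits with the focus on Day 28, Day 56, and Day 84", adds change from baseline, and then states: "Frequency counts of new or worsening abnormalities will also be provided". It does not say which values are eligible, what counts as an abnormality, or whether the count is per visit or per dose period. These counts carry weight, because SAP 8 states: "The safety analysis will be based primarily on the frequency of new or worsening adverse events, laboratory abnormalities, and SAEs".

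Protocol Appendix E creates the unscheduled values. "Patients with new or unexplained muscle symptoms should have an unscheduled visit scheduled within 7 days of site notification", with a full chemistry panel. Signs or symptoms of hepatitis, CK above 10 times the upper limit of normal (ULN) and ALT above 3 times ULN also lead to unscheduled visits. The appendix provides for a temporary stop of study drug in some of these cases.

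**The concern.** A selection rule suited to by-visit means is a poor rule for counting toxicity. A mean at Day 56 should rest on comparable, planned samples. A count of patients with an abnormality should rest on the worst value that each patient had. If the same rule drives both, a value drawn because a patient felt unwell is set aside whenever a planned sample exists for that window. The planned sample may come after study drug was interrupted. The fallback leans the same way: within a run of repeat tests, the last value is more likely to be the recovered one than the peak.

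At stake is the accuracy, by dose, of a table that the SAP names among the main bases of the safety analysis. Safety data are also one of the inputs to dose confirmation under the secondary objectives.

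**Working it through.** The plan states no figure that depends on this rule, so there is nothing to reproduce. The check sets the sections side by side and then sizes one omitted patient.

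**1. Does the rule reach the abnormality counts?** SAP 5.2 opens by saying that it concerns summaries of laboratory variables, and no other section selects laboratory values. SAP 8.3 puts the counts in a sentence of their own and gives no eligible values. SAP 7.2 uses the term descriptive statistics to include counts and percentages. A programmer could therefore reasonably apply 5.2 to the counts. The text permits this reading but does not compel it.

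**2. Which values are exposed?**
- Symptom-triggered visits (muscle symptoms, suspected hepatitis): the first abnormal value can arise at the unscheduled visit. Exposed.
- CK above 10 times ULN or ALT above 3 times ULN: an elevation has already been seen, often on a scheduled sample, since chemistry is drawn at every study visit. That first value is kept. A higher value on repeat testing is exposed.
- Creatinine or GFR change (protocol 9.1.4.2): a finding at any visit leads to repeat chemistry. The position is the same as for CK and ALT.
- Scheduled value missing: an unscheduled value is used, but the last one, so an earlier peak in the window is exposed.

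**3. How long are the gaps?** On-treatment chemistry falls on Days 14, 28, 42, 56, 70 and 84, nominally 14 days apart. With the ±3 day visit window that applies through Day 70, two successive samples up to that visit can be 14 + 3 + 3 = 20 days apart. A rise and recovery between planned samples is possible.

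**4. Where else would the peak appear?** In listings and narratives, always. In the TEAE tables of SAP 8.2, under the dose at onset, if it is reported as an adverse event. Protocol 9.1 makes clinically significant laboratory abnormalities adverse events whatever the type of visit. It leaves significance to the investigator, does not require a result to be reported if repeat testing does not verify it, and prefers a diagnosis to separate signs. The size of a CK or ALT rise may therefore not show in a TEAE table. The SAP plans no shift table, worst-value table or threshold count that would recover it.

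**5. Scale.** One patient left out of a count moves the rate by 1/8 = 12.5 percentage points. With the 6 completers that protocol 4.3 aims to secure, it moves by 1/6 = 16.7 points.

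**6. Illustration only (invented case).** CK is 12 times ULN at an unscheduled Day 49 visit, drug is held, and the scheduled values on Days 42 and 56 are normal.
- SAP 5.2 applied to the counts: 0/8 at 600 mg. Exact 95% upper limit = 1 − 0.025^(1/8) = 36.9%.
- All values used: 1/8 = 12.5%. Lower limit = 1 − 0.975^(1/8) = 0.3%. The upper limit solves (1 − p)^8 + 8p(1 − p)^7 = 0.025, giving 52.7%.

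The two intervals overlap widely. What changes is whether the table shows an event at that dose at all.

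**The case against.** A reader might infer that peak toxicity values never reach the safety counts, or that abnormality rates are known to be biased downward. The documents do not support either statement, for four reasons.

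- The scheduled-value rule names descriptive and summary statistics, while the counts are a separate sentence in SAP 8.3. That is silence, not an exclusion. Mock-up tables and derived-data specifications are kept in stand-alone documents (SAP 5.4) and may settle it.
- Confirmed, clinically significant abnormalities are also adverse events and are counted by dose. In the Day 49 case, a CK rise that led to a drug hold would very likely be reported. The contrast of 0/8 with 1/8 then concerns one laboratory table under one reading.
- Many CK, ALT and creatinine triggers would first be seen on a scheduled sample, which the rule keeps.
- With about 8 open-label patients, the listings can be read in full. Dose confirmation also draws on efficacy, PK, earlier studies and GEM-301, and no section says that it rests on the abnormality table.

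All four stand, and they limit the harm. They do not close the gap. SAP 8 lists laboratory abnormalities separately from adverse events as a main basis of safety, so the adverse event route, which depends on investigator judgment, does not replace a defined laboratory count. Leaving the choice to programming specifications is also weaker than stating it in the SAP. The study is open-label, and SAP 10 records an interim look at adverse events, with a January 2017 cut-off, before the SAP was signed in June 2017.

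**Conclusion.** The concern holds as a gap with a likely direction, not as a demonstrated bias. The only stated selection rule takes scheduled values, or else the last unscheduled value, and the abnormality counts are not exempted. Applied as written, peaks found at symptom-triggered visits, or later on repeat testing, can be missing from the laboratory abnormality tables.

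Each patient so omitted costs 12.5 percentage points with 8 patients, or 16.7 with 6. How many patients would be affected cannot be known from the documents. The conclusion assumes that SAP 5.2 is applied to the counts in 8.3, and that the patient has no equally abnormal scheduled value in the same dose period. Listings, narratives and TEAE reporting reduce the consequence. The change is worth making because it is cheap and concerns a named basis of the safety analysis.

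**What to change.** Keep the scheduled-value rule for by-visit means and change from baseline. Add to SAP 5.2 and 8.3 that counts of new or worsening abnormalities use the worst post-baseline value per patient within each dose period, taken from all scheduled, unscheduled and repeat measurements, with confirmed laboratory errors excluded. This supplements protocol 10.2.2 and does not contradict it.

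Optionally, add counts of patients reaching cut-offs that the protocol already uses: creatinine rise above 0.3 mg/dL, estimated GFR fall above 15 mL/min, hemoglobin fall above 1.5 g/dL, CK above 3 and 10 times ULN, and ALT above 3, 5 and 8 times ULN. In the protocol, AST above 3 or 5 times ULN matters only with further conditions (bilirubin, INR or symptoms for the former, duration for the latter). If counted alone, these should be labelled as added summary cut-offs.

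Cost: SAP wording and one extra table. Unscheduled and repeat values are already recorded in the clinical database, and SAP 1 allows revision before database lock. The downside is that the counts may look slightly less favourable.

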### **5.3 Handling of Dropouts and Missing Data**

The primary analyses of the primary and secondary outcome variables will use linear mixed effects models. This analysis method will allow for inclusion of patients with missing values thus using the maximum amount of data for the analysis and making fewer assumptions about the missing data compared to a more traditional per-protocol analysis.

Adverse events with missing start dates will be considered as treatment-emergent unless the partial date excludes that possibility, e.g. the adverse event month is prior to the treatment infusion month. Otherwise, the first day of the month will be used to impute missing start days and January will be used to impute missing start months.

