9 SAFETY ASSESSMENTS

9.1 Adverse Events

An adverse event is defined as any untoward medical occurrence in a clinical investigation patient administered a pharmaceutical product, which does not necessarily have a causal relationship with this treatment. An adverse event can therefore be any unfavorable and/or unintended sign (including an abnormal laboratory finding), symptom, or disease temporally associated with the use of an investigational medicinal product, whether or not related to the investigational medicinal product. All adverse events, including observed or volunteered problems, complaints, or symptoms, are to be recorded on the appropriate eCRF.

Adverse events, which include abnormal and clinically significant clinical laboratory test variables, will be monitored and documented from the time of first dose of study drug (Day 1) until study participation is complete (the Follow-up Visit). Patients should be instructed to report any adverse event that they experience to the Investigator. Beginning with the signing of the informed consent until the time of the first dose of study drug (Day 1), investigators should make updates to medical history and record any pre-existing medical condition or signs or symptoms that changes in severity, frequency, or seriousness in the medical history. Serious adverse events that occur prior to the first dose of study drug (Day 1) should be reported as an update to medical history as well as be reported on the appropriate adverse event eCRF. Beginning with the first dose of study drug (Day 1), investigators should make an assessment for adverse events at each visit and record all adverse events, non-serious and serious, on the appropriate adverse event eCRF.

Wherever possible, a specific disease or syndrome rather than individual associated signs and symptoms should be identified by the Investigator and recorded on the eCRF. However, if an observed or reported sign or symptom is not considered a component of a specific disease or syndrome by the Investigator, it should be recorded as a separate adverse event on the eCRF. Additionally, the condition that led to a medical or surgical procedure (e.g., surgery, endoscopy, tooth extraction, or transfusion) should be recorded as an adverse event, not the procedure. Concomitant procedures should be recorded as such on the appropriate eCRF.

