### 2.2 Trial Design

This is a Phase 2, open-label, dose-finding, 3-period, 3-treatment study using successively escalating doses of 300 mg, 600 mg, and 900 mg gemcabene in patients with HoFH. All patients will be on each of the successive doses for 4 weeks at a time. Patients will remain on their current

stable, lipid-lowering therapy throughout the study. Patients will not be allowed in the study if they are undergoing apheresis or taking mipomersen or lomitapide.

The population for this study is male and female patients,  $\geq 17$  years of age, diagnosed with HoFH by genetic confirmation or a clinical diagnosis based on either (1) a history of an untreated LDL-C concentration  $>500$  mg/dL (12.92 mmol/L) together with either appearance of xanthoma before 10 years of age, or evidence of heterozygous familial hypercholesterolemia in both parents or, if history is unavailable, (2) LDL-C  $>300$  mg/dL (7.76 mmol/L) on maximally tolerated lipid-lowering drug therapy. Approximately 8 patients will be enrolled into the study. Total study duration will be up to 18 weeks and will consist of a Screening Visit, a Treatment Period, and a Follow-up Visit.

The Treatment Period is a sequential design whereby each patient will receive gemcabene 300 mg QD for 4 weeks. The same patients will then receive a 600 mg dose QD for 4 weeks and finally 900 mg dose QD for 4 weeks. There will be no interruptions in gemcabene dosing when changing from the 300 mg to the 600 mg dose or when changing from the 600 mg to the 900 mg dose unless there are clinically significant safety issues resulting in the temporary or permanent discontinuation of study drug. The first 300 mg dose of study drug will be administered at the site on Day 1. Assessments will be performed after the patient has been on the study drug for 2 weeks for each dosing level and on the last day of each dose.

The Follow-up Visit will occur 4 weeks ( $\pm 3$  days) after the last dose of study drug.

The schedule of events for the trial is provided in Table 1.

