## **8.2 Adverse Events**

AEs will be coded using the most recent version of the Medical Dictionary for Regulatory Activities (MedDRA) and summarized by treatment group, system organ class, and preferred term.

A summary overview of TEAEs will be provided which presents the number and percentage of patients in each treatment group satisfying each of the following categories:

- All TEAEs,
- Drug-related TEAEs,
- Maximum severity of TEAEs,
- Maximum severity of drug-related TEAEs,
- All treatment-emergent SAEs,
- Drug-related treatment-emergent SAEs,
- Death due to TEAEs,
- TEAEs leading to study drug discontinuation, and
- Drug-related TEAEs leading to study drug discontinuation.

The numbers and percentages of patients with TEAEs will be summarized by MedDRA preferred term within system organ class, by treatment group and overall. For the summaries by treatment group, multiple AEs with the same MedDRA preferred term within system organ class from the same patient within a given treatment will only be counted once. For overall summaries, multiple AEs with the same MedDRA preferred term within system organ class from the same patient will only be counted once. The AE onset date will determine the treatment group classification for the AE.

All TEAEs related to study drug, SAEs, and AEs leading to study drug discontinuation will be summarized in the same manner. Summaries will also be provided for the numbers and percentages of patients by system organ class, preferred term, and maximum severity, for TEAEs and drug-related TEAEs.

All AEs will be included in by-patient listings containing additional information of interest such as onset and resolution times, maximum severity, causal relationship to study medication, and action taken. Specific by-patient listings of SAEs and TEAEs leading to study discontinuation will be provided.

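### SAP 5.3 imputes partial AE start dates backwards with no floor at first dose, so under SAP 8.2 an event kept as treatment-emergent can fall before Day 1 or on a lower dose, never a higher one

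*SAP*

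**What the plan says.** **Imputation.** SAP 5.3 says that AEs with missing start dates "will be considered as treatment-emergent unless the partial date excludes that possibility". The next sentence opens with *Otherwise* and states that "the first day of the month will be used to impute missing start days and January will be used to impute missing start months". Nothing limits the imputed date to the date of first dose or to the start of a dose period. The example in the same paragraph compares the event month with the month of an infusion, although gemcabene is an oral tablet.

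**Dose assignment.** SAP 8.2: "The AE onset date will determine the treatment group classification for the AE". It has no separate rule for imputed dates. Repeat events with the same preferred term "from the same patient within a given treatment will only be counted once".

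**Definition.** SAP 3.2.1 makes an AE treatment-emergent if it occurs on or after the first dose. SAP 5.2 gives earlier dates a negative study day. Protocol 9.1 records non-serious AEs only from the first dose; before that, changes go to medical history.

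**Design.** Each patient takes 300, 600 and 900 mg in that order for 4 weeks each. SAP 2.2: "There will be no interruptions in gemcabene dosing when changing from the 300 mg to the 600 mg dose". The same holds from 600 to 900 mg, except for interruptions for clinically significant safety issues.

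**Elsewhere.** SAP 5.4 leaves derived-database specifications to stand-alone documents, which are not available here.

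**The concern.** First-of-month imputation is common and, with a treatment-emergent default, usually cautious. Here the onset date has a second job: it decides which dose the event counts against. A date pulled backwards in an ascending design can only credit the event to an earlier and lower dose, or to no dose at all. The error therefore has a direction, away from the higher doses. Safety data are one of the inputs named in the secondary objective of confirming the Phase 3 dose.

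The pre-Day-1 case is also an internal contradiction. SAP 5.3 calls the event treatment-emergent, its imputed date fails the SAP 3.2.1 definition, and SAP 8.2 has no column for it.

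**Working it through.** The plan gives no figure to reproduce, so the check applies the two rules as written.

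**Direction.** The first of the month (or January of the same year) is never later than the true date. Dose never falls over time in this design. Hence the imputed dose is never above the true dose.

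**Example** (first dose on 15 June 2016, an assumed date):

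| True onset | True day and dose | Imputed date | Imputed day | Result |
|---|---|---|---|---|
| 20 June | Day 6, 300 mg | 1 June | Day -14 | no dose |
| 20 July | Day 36, 600 mg | 1 July | Day 17 | 300 mg |
| 17 August | Day 64, 900 mg | 1 August | Day 48 | 600 mg |

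**Frequency, missing day only.** From the documents: dose periods are Days 1-28, 29-56 and 57-84. Assumed: first-dose dates uniform over 1 March 2016 to 28 February 2017 (365 dates) and onset uniform over Days 1-84. That is 365 × 84 = 30,660 cases, each classified by its imputed date.

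| | As written | With a floor at first dose |
|---|---|---|
| Same dose | 47.7% | 65.1% |
| Lower dose | 34.8% | 34.9% |
| Before Day 1 | 17.5% | 0% |
| Higher dose | 0% | 0% |

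Leaving the true period: 100 − 47.7 = 52.3%. All 366 dates of 2016 give 34.8% lower and 17.6% before Day 1.

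**How firm is the 52%?**
- By single first-dose date it runs from 3.6% to 97.6%. Averaged over 8 random first-dose dates, the 95% range is about 35% to 69%.
- Moving the dose changes and end of treatment within the visit windows gives 51.3% to 53.9%.
- Onset two or three times as frequent in the first 14 days of each dose gives 60.0% or 63.8%; in the last 14 days, 44.7% or 40.8%.

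**Missing day and month.** 88.4% fall before Day 1, 7.7% on a lower dose and about 4% stay. With a floor, nearly all go to 300 mg: true 300 mg events are then right, while 96.0% of true 600 and 900 mg events are wrong, so (0 + 96.0 + 96.0)/3 = 64.0% sit on a lower dose.

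**Expected number** (AE rates and missing-day shares are assumed; the documents give neither): 8 patients × AEs per patient × share with a missing day × 0.523.
- Low: 8 × 1 × 0.02 × 0.523 = 0.08
- Middle: 8 × 3 × 0.05 × 0.523 = 0.63
- High: 8 × 5 × 0.10 × 0.523 = 2.09

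**Effect of one misplaced event.** Planned enrolment is about 8. Protocol 4.3 does not replace withdrawals unless there are more than two, so a column may hold 8 − 2 = 6 patients. A row moves by 1/8 = 12.5 points to 1/6 = 16.7 points. If the event leaves one dose column and enters another, the contrast between them moves by up to 2/8 = 25 to 2/6 = 33.3 points. A column does not change if the patient already counts in that row and column through another event.

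**The case against.** **The text may not mean this.** *Otherwise* could cover only events already ruled out as treatment-emergent, and the imputation would then not touch treatment-emergent events. That reading cannot be excluded. But it leaves a partial-date treatment-emergent event with no onset date, so SAP 8.2 could not assign it a dose. The sentence needs repair on either reading.

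**Few events are at risk.** This stands. Protocol 11.1.5 sends missing data back to the site as queries. Protocol 9.1 says "investigators should make an assessment for adverse events at each visit", and visits are about two weeks apart on treatment, so most start dates should be complete.

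**The result can be checked.** SAP 8.2: "All AEs will be included in by-patient listings containing additional information of interest such as onset and resolution times". Listings let a reader spot a misplaced event, but they do not correct the by-dose tables.

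**The specifications may contain a floor.** Possible. However, a program that follows SAP 5.3 as written reproduces the problem, and a rule that decides dose attribution belongs in the SAP.

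**Stronger readings that the documents do not support.**
- A reader might infer that treatment-emergent events drop out of the overall count. SAP 5.3 sets the flag from the partial date, not the imputed one, so overall counts are largely protected.
- A reader might infer that the safety comparison between doses is seriously distorted. The direction is certain, but the likely number is around one event or fewer, the AE tables are descriptive, no decision rule uses them, and dose is already confounded with time in a single ascending sequence without a control.
- A reader might infer that every ambiguous event must leave the dose columns. That is a trade-off, costed under the fix.

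**Conclusion.** The rule as written gives a wrong result for some events: a pre-Day-1 onset for an event that the SAP itself keeps as treatment-emergent, or a lower dose than the one being taken. It never errs towards a higher dose. This rests on the natural reading of *Otherwise*, and on SAP 8.2 using the imputed date as the onset date.

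The 52% is conditional on a missing day and on uniform onset and start dates. With about 8 patients the realised share could lie far from it. The expected count of 0.1 to 2.1 events rests wholly on assumed AE and missing-date rates. It is a minor correction, worth making because it is cheap and because one event can be a visible fraction of a column of 6 to 8 patients.

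**What to change.** **In SAP 5.3:**
1. Say explicitly that the imputation applies to AEs not excluded as treatment-emergent, and that for these the imputed start date is the later of the first-of-month (or January) date and the date of first dose.
2. Replace the reference to the infusion month with the month of first dose.

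**In SAP 8.2:** because the floor still leaves about 35% of missing-day events on a lower dose, flag each AE with an imputed date whose possible onset interval spans a dose change. Show the flag in the listings and as a table footnote or a sensitivity count.

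**Optional:** a column for dose at onset undetermined, best limited to cases where the visit of first report is captured. Its cost, as the share of missing-day events leaving the dose columns:

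| Information used | Time after Day 84 counted as a further period | Three dose periods only |
|---|---|---|
| Reported at the next visit | 34.9% | 34.9% |
| Reported one visit late | 70.9% | 59.2% |
| Calendar month alone | 83.9% | 68.1% |

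In the first row the events removed are exactly those that the floor alone would misplace. On calendar month alone, 83.9 − 34.9 = 49.0 points (68.1 − 34.9 = 33.2 on three periods) would have been placed correctly, so the column then costs more than it gains.

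**Cost of the main fix:** a few SAP sentences and a little programming, with no new data. SAP 1 allows revision before database lock, with the reasons given in the study report.
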